8.3 Unscheduled Visits

Aside from scheduled visits, subjects may require **Unscheduled Visits (UV)** either by telephone or in person at the clinical study site. This visit will include:

- Review of concomitant medications
- Assessment of adverse events
- Assessment of complaints and/or device deficiencies
- Data review by clinician to ensure that subject was delivering boluses according to the correct study phase
- Upload BG and ketone meter data (if visit is conducted in person at the clinical study site)

All UVs must obtain the defined schedule of assessments. Additional assessments may be warranted at the discretion of the investigator. UVs should not be documented for appointment confirmation, device shipments, general inquiries, or for activities covered by other assessments.

8.4 Early Withdrawal

Any subject may withdraw early from the study at any time for any reason. The investigator may also terminate a subject's participation in the study if it is in the

best interest of the subject or if the sponsor or local regulatory agency (e.g., FDA) terminates the study. Upon withdrawal, assessments will be performed according to the Table 1: Schedule of Assessments. This visit will include:

- Review of concomitant medications
- Assessment of vital signs (if visit is conducted in person at the clinical study site)
- Assessment of adverse events
- Return of devices (if not commencing or recommencing their participation in the Omnipod Horizon™ Pivotal Study (G190270). Subjects aged 2-5.9 may hold onto their devices if continuing onto the Pivotal study, but must agree to return to using their standard therapy for the Pivotal study Standard Therapy Phase)
- Assessment of complaints and/or device deficiencies
- Data review by clinician ensure that subject was delivering boluses according to the correct study phase
- Upload BG and ketone meter data (if visit is conducted in person at the clinical study site)

An early withdrawal visit should be conducted at the clinical study site when possible. The subject will be requested to return their study devices to the site, the reason for withdrawal will be recorded, and their participation in the study will end.

In the event of a subject's death during the study, the subject's participation will be considered terminated and the date of death will be used as the date of study exit.

8.5 Lost to Follow-up

Every effort will be made to contact a subject in the event of a missed scheduled visit. A subject will be considered lost to follow-up if they are inaccessible by two or more different methods of contact and fail to show up for two scheduled visits. The site will document each attempt made to contact the subject and specify the reason for early withdrawal as lost to follow-up.

9 SPONSOR REPRESENTATIVES

One or more representatives of the Sponsor may be present at the clinical study site visits under supervision of the investigator.

10 SAFETY

10.1 Types of Known Risks and Benefits

There are known risks and benefits. Most of the risks are not unique to the study and are typical for patients using insulin pumps, CGM, and BG meters.

The known risks are as follows:

- Hypoglycemia and/or hyperglycemia as a result of change in diet, activity, diabetes management or insulin regimen during the study.
- Hypoglycemia and/or hyperglycemia as a result of over or under delivery of insulin due to a device defect, failure or malfunction of any of the system components.
- Hypoglycemia, hyperglycemia, diabetic ketoacidosis, seizure, coma or death related to insulin administration, pump use or misuse, or Horizon™ System use or misuse or malfunction.
- Use of the Pod (Omnipod® tubeless, insulin delivery pump) - Because the Pod uses only rapid-acting insulin, users are at increased risk for developing hyperglycemia if insulin delivery is interrupted. If it is untreated, prolonged hyperglycemia can quickly lead to diabetic ketoacidosis (DKA). DKA can cause symptoms such as breathing difficulties, shock, coma, or death. Further, occlusions can interrupt insulin delivery and lead to hyperglycemia or DKA. Other potential risks associated with using the Pod are:
 - Anaphylaxis (allergic shock)
 - Bruising at the Pod site
 - Bleeding at the Pod site
 - Erythema (redness at the Pod site)
 - Excoriation (raw skin at Pod site)
 - Pruritus (itching)
 - Induration (hardening of the skin at the Pod site)
 - Infection (can include heat, redness, swelling, pain, and drainage)
 - Inflammation (redness, swelling)
 - Skin reaction to adhesive at the Pod site
 - Papule (small, solid raised area on the skin similar to a pimple)
 - Pain or discomfort
 - Ulceration (skin sores)
 - Vesicles (blisters)
- Use of the CGM - risk of bruising, infection, pain and/or bleeding at the site of insertion, and skin site reaction to adhesive
- On rare occasions, the CGM sensor may break and leave a small portion of the sensor under the skin that may cause redness, swelling, or pain at the insertion site, and may require surgical removal.
- Blood sampling with fingerstick - minor discomfort and risk of infection at site of fingerstick

There are potential benefits from this study. The Omnipod Horizon™ CGM-informed bolus calculator is intended to utilize both CGM value and trend to deliver a safe correction bolus and improve ease of use.

10.2 Hypoglycemia/Hyperglycemia

Subjects will be asked to treat per their usual routine if they suspect either hypoglycemia or hyperglycemia, either by confirmation of hypoglycemia with a fingerstick BG, symptoms, or perceived risk.

Subjects will be encouraged to manage their hyperglycemia per their usual routine. This includes checking for ketones using the study-approved ketone meter and administering a correction bolus if needed.

In the event of unexplained hyperglycemia, where the CGM is >300 mg/dL for ≥ 1 hour or >250 mg/dL for ≥ 2 hours, blood glucose (measured with BG meter) and ketones should be checked. If BG is ≥ 300 mg/dL and ketones are >1.0 mmol/L, an occlusion or dislodged cannula should be suspected. The Pod should be removed, and the subject will be instructed to replace the Pod. Subjects should contact the clinical site for further instructions to determine whether an additional injection of insulin is required.

10.3 Adverse Events

10.3.1 Definitions

Adverse Event (AE): is defined as any untoward medical occurrence, unintended disease or injury, or any untoward clinical signs (including an abnormal laboratory finding) in subjects, users or other persons, whether or not related to the investigational medical device.

NOTE 1: This includes events related to the investigational medical device or the comparator.²⁸

NOTE 2: This definition includes events related to the procedures involved (any procedure in the clinical investigation plan).²⁸

Serious Adverse Event (SAE): Any untoward medical occurrence that:

- Led to death
- Led to serious deterioration in the health of the subject, that either resulted in:
 - a life-threatening illness or injury, or
 - a permanent impairment of a body structure or a body function, or
 - in-patient or prolonged hospitalization, or
 - medical or surgical intervention to prevent life-threatening illness or injury or permanent impairment to a body structure or a body function.
- Led to fetal distress, fetal death, or a congenital abnormality or birth defect.

NOTE: Planned hospitalization for a pre-existing condition, or a procedure required by the clinical investigational plan, without serious deterioration in health, is not considered a serious adverse event.²⁸

Unanticipated Adverse Device Effect (UADE): Any serious adverse effect on health or safety or any life-threatening problem or death caused by, or associated with, a device, if that effect, problem, or death was not previously identified in nature, severity, or degree of incidence in the investigational plan or application (including a supplementary plan or application), or any other unanticipated serious problem associated with a device that relates to the rights, safety, or welfare of participants.²⁸

Adverse Device Effect (ADE): An adverse device effect (ADE) is an adverse event related to the use of an investigational medical device.²⁸

NOTE 1: This definition includes any adverse event resulting from insufficient or inadequate instructions for use, deployment, implantation, installation, or operation, or any malfunction of the investigational medical device.²⁸

NOTE 2: This definition includes any event resulting from user error or from intentional misuse of the investigational medical device.²⁸

An event that occurs solely due to participant (i.e., user) error in which the device functions properly generally will not be considered an ADE unless it is determined that the instructions on the screen of the device or user manual (or similar training materials) may have contributed to the event (note: the event may still meet criteria for reporting as an adverse event).

Serious Adverse Device Effect (SADE): A serious adverse device effect is defined as an adverse device effect that has resulted in any of the consequences characteristic of a serious adverse event.²⁸

Device Deficiency (DD): A device deficiency is defined as a device related complaint or malfunction or any inadequacy of a device with respect to its identity, quality, durability, reliability, safety or performance and includes misuse or use errors and inadequate labeling. A device deficiency is something that happens to a device or is related to device performance, whereas an adverse event happens to a participant. A device deficiency may occur independently from an AE, or along with an AE. An AE may occur without a device deficiency or there may be an AE related to a device deficiency.

Note: for reporting purposes, sites will not be asked to distinguish between device complaints and malfunctions.

For any event where there is suspicion that the study device is involved, the Sponsor will request that the investigator return the device for evaluation.

All device complaints or malfunctions involving any investigational component of the Omnipod Horizon™ System used in the study will be reported to the Sponsor within 5 business days of knowledge of the deficiency and documented on an appropriate eCRF. All study product associated with a reported device deficiency (PDM, Pod, and CGM) should be retained at the clinical site and returned to the Sponsor or CGM manufacturer for investigation and analysis.

10.3.2 Reportable Adverse Events

Adverse events will be assessed on an ongoing basis throughout the study. Adverse event reporting will begin at the time of enrollment (i.e., insertion of the CGM sensor) and continue until the subject's participation has ended. All adverse events must be followed until resolution, or until the AE has stabilized, or until the study has been completed.

Pre-existing medical conditions or symptoms observed prior to enrollment will not be recorded as an AE and should be collected in the subject's medical history. In the event there is a change (i.e., worsening) in the pre-existing medical condition or symptoms after enrollment meeting the criteria of a reportable adverse event, then an AE must be reported.

For this protocol, a reportable adverse event includes any untoward medical occurrence that meets one of the following criteria:

1. An SAE
2. An ADE unless excluded from reporting in Hypoglycemic Events and Hyperglycemic/Ketotic Events sections below
3. An AE occurring in association with a study procedure
4. An AE not related to a study device issue which leads to temporary or permanent discontinuation of the study device
5. An AE that affects the participant's ability to complete any study procedures
6. An AE for which a visit is made to a hospital emergency department
7. Hypoglycemic Events as defined below
8. Hyperglycemia/Ketotic Events as defined

Skin reactions from sensor or pod placement are only reportable if severe and/or required treatment.

For the purpose of this protocol, mild symptoms of hypoglycemia and hyperglycemia (i.e., clinically non-significant) or blood glucose values out of the normal range (whether or not they resulted in delayed meals or correction boluses) will not be reported as AEs unless determined to meet the reportable criteria in the Hypoglycemic Events and Hyperglycemic/Ketotic Events sections below.

All reportable AEs—whether volunteered by the participant, discovered by study personnel during questioning, or detected through physical examination, laboratory test, or other means—will be reported on an AE eCRF.

10.3.3 Hypoglycemic Events

Hypoglycemia is only reportable as an adverse event when one of the following criteria is met:

- Severe Hypoglycemia: The event required assistance of another person due to altered consciousness, and required another person to actively administer carbohydrate, glucagon, or other resuscitative actions²⁵ This means that the participant was impaired cognitively to the point that he/she was unable to treat himself/herself, was unable to verbalize his/her needs, was incoherent, disoriented, and/or combative, or experienced seizure or loss of consciousness. These episodes may be associated with sufficient neuroglycopenia to induce seizure or loss of consciousness. If plasma glucose measurements are not available during such an event, neurological recovery attributable to the restoration of plasma glucose to normal is considered sufficient evidence that the event was induced by a low plasma glucose concentration.
- Hypoglycemia resulting in an SAE that may not otherwise meet the definition of Severe Hypoglycemia defined above.

When a hypoglycemic event meets the above reporting requirements, an Adverse Event Form should be completed. A severe hypoglycemia event should be considered a serious adverse event and follow the SAE reporting requirements.

10.3.4 Hyperglycemic/Ketotic Events

Hyperglycemia is only reportable as an adverse event when any of the following criteria is met:

- The event involved DKA, as defined by the Diabetes Control and Complications Trial (DCCT)²⁴ and described below
- Evaluation or treatment was obtained at a health care provider facility for an acute event involving hyperglycemia or ketosis, or the participant contacted the site and received guidance on how to manage the hyperglycemia/ketosis
- Prolonged hyperglycemia: defined as meter BG ≥ 300 mg/dL and ketones >1.0 mmol/L
- Hyperglycemia resulting in an SAE that may not otherwise meet the above criteria

Hyperglycemic events are classified as DKA²⁴ if all of the following are present:

- Symptoms such as polyuria, polydipsia, nausea, or vomiting;
- Serum ketones >1.5 mmol/L or large/moderate urine ketones;
- Either arterial blood pH <7.30 or venous pH <7.24 or serum bicarbonate <15 ; and
- Treatment provided in a health care facility

When a hyperglycemia/ketotic event meets the above reporting requirements, Adverse Event Form should be completed.

Events meeting DKA criteria should be considered a serious adverse event and follow the SAE reporting requirements. Hyperglycemia events not meeting criteria for DKA generally will not be considered as serious adverse events unless one of the SAE criteria above is met.

10.3.5 Relationship of Adverse Event to Investigational Device

The investigator will be responsible for making a determination on the causal relationship of the AE. Specifically, the investigator will report whether the AE was related to study procedures and/or related to the investigational device.

To ensure consistency of adverse event causality assessments, investigators should apply the following general guideline when determining whether an adverse event is related.

The causal relationship to the study procedures and the investigational device for each adverse event will be rated as follows:

- Unrelated: The event is not related to the procedures or the investigational device.
- Possibly Related: The temporal sequence is such that the relationship is not unlikely or there is no contradicting evidence that can reasonably explain the subject's condition. There is a possibility of any relation between the event and the procedures or the investigational device.
- Related: The temporal sequence is relevant or the event abates upon completion of the procedure/ investigational device, or the event cannot be reasonably explained by the subject's condition or comorbidities. The event is related or most likely associated with the procedures or the investigational device.

10.3.6 Severity (Intensity) of Adverse Events

The severity (intensity) of an adverse event will be rated on a three-point scale: (1) mild, (2) moderate, or (3) severe. A severity assessment is a clinical determination of the intensity of an event. Thus, a severe adverse event is not necessarily serious. For example, itching for several days may be rated as severe, but may not be clinically serious.

- **MILD**: Usually transient, requires no special treatment, and does not interfere with the participant's daily activities.
- **MODERATE**: Usually causes a low level of inconvenience, discomfort or concern to the participant and may interfere with daily activities but is usually ameliorated by simple therapeutic measures and participant is able to continue in study.
- **SEVERE**: Interrupts a participant's usual daily activities, causes severe discomfort, may cause discontinuation of study device, and generally requires systemic drug therapy or other treatment.

10.3.7 Outcome of Adverse Events

The outcome of each reportable adverse event will be classified by the investigator as follows:

- **RECOVERED/RESOLVED** - The participant recovered from the AE/SAE without sequelae. Record the AE/SAE stop date.

- RECOVERED/RESOLVED WITH SEQUELAE - The event persisted and had stabilized without further anticipated change in the event status. Record the AE/SAE stop date.
- FATAL - A fatal outcome is defined as the SAE that resulted in death. Only the event that was the cause of death should be reported as fatal. AEs/SAEs that were ongoing at the time of death; however, were not the cause of death, will be recorded as "resolved" at the time of death.
- NOT RECOVERED/NOT RESOLVED (ONGOING) - An ongoing AE/SAE is defined as the event was ongoing with an undetermined outcome.
 - An ongoing outcome will require follow-up by the site in order to determine the final outcome of the AE/SAE or until participant completes the study.
 - The outcome of an ongoing event at the time of death that was not the cause of death, will be updated and recorded as "resolved" with the date of death recorded as the stop date.
- UNKNOWN - An unknown outcome is defined as an inability to access the participant or the participant's records to determine the outcome (for example, a participant that was lost to follow-up).

If any UADEs are ongoing when a participant completes the study (or withdraws), the subject will continue to be followed until the event resolves or has no prospect of improvement or change, even after the participant has completed all applicable study visits/contacts, unless that subject has withdrawn their consent. For all other reportable adverse events, data collection will end at the time the participant completes the study. Note: Participants should continue to receive appropriate medical care for an adverse event after their participation in the study ends.

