8.2.3 Visit 6 (End of Study)

Visit 6 will be conducted either over the telephone or in person at the clinical study site on Day 14 ±1d. This visit will include:

- Review of concomitant medications
- Assessment of vital signs (if visit is conducted in person at the clinical study site)
- Assessment of adverse events
- Return of devices (if not commencing or recommencing their participation in the Omnipod Horizon™ Pivotal Study (G190270). Subjects aged 2-5.9 may hold onto their devices if continuing onto the Pivotal study, but must return to using their standard therapy for the Pivotal study Standard Therapy Phase.)
- Assessment of complaints and/or device deficiencies
- Data review by clinician to ensure that subject was delivering boluses as instructed during Visit 4
- Upload BG and ketone meter data (if visit is conducted in person at the clinical study site)

This visit will mark the end of this study for each subject.

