10.6 Stopping Criteria

10.6.1 Participant Discontinuation of Study Participation

In the case of a UADE, the Medical Monitor will determine if the use of the study device will be suspended while the problem is diagnosed. The use of the study device may continue if the Medical Monitor believes the event is explainable, unlikely to reoccur and that it is safe for the subject to continue using the device. Alternately, the Medical Monitor may request the study subject, or all study subjects, to stop using the study device or to only use in Manual Mode. Should all study subjects be required to stop using the study device or to only use in Manual Mode due an UADE, use of the study device or Automated Mode will not be restarted until approval is received from the IRB, DSMB and FDA.

Use of the study device by a participant will be discontinued if any of the following occur:

- The investigator believes it is unsafe for the participant to continue on the intervention. This could be due to the development of a new medical

condition or worsening of an existing condition; or participant behavior contrary to the indications for use of the device that imposes on the participant's safety.

- The participant requests that the treatment be stopped
- Participant pregnancy
- Two distinct episodes of DKA as defined above
- Two distinct severe hypoglycemia events as defined above
- One episode of DKA and one severe hypoglycemia event as defined above

An additional requirement for continued study device use following a single DKA or severe hypoglycemia event will be that (1) the site investigator believes that the event is explainable, unlikely to recur, and that it is safe for the participant to continue to use the system and (2) the Medical Monitor concurs. If the Medical Monitor determines that the occurrence of the event indicates that it is not safe for the participant to continue to use the system, use will be discontinued, and the subject will be withdrawn from the study.

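### Follow-up past a subject's last visit is reserved for UADEs, so a serious device-related event still open at Visit 6 may keep no final outcome, and sections 10.3.2 and 10.3.7 word the end of follow-up differently

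*Combined protocol and SAP*

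**What the plan says.** Section 10.3.7 has two rules for events still open when a subject leaves the study.

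- For UADEs: "If any UADEs are ongoing when a participant completes the study (or withdraws), the subject will continue to be followed until the event resolves", or until no further change is expected, unless consent has been withdrawn.
- For everything else: "For all other reportable adverse events, data collection will end at the time the participant completes the study".

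The same section gives the site's duty for an open event: "An ongoing outcome will require follow-up by the site in order to determine the final outcome of the AE/SAE or until participant completes the study". Its label for such an event is the not recovered/not resolved category: "An ongoing AE/SAE is defined as the event was ongoing with an undetermined outcome".

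Section 8.2.3 fixes the time point. Of Visit 6, on Day 14 ±1, it says: "This visit will mark the end of this study for each subject". Table 1 schedules no later safety contact.

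Section 10.3.2 sets the limit in other words. Adverse event reporting stops when the subject's participation ends, but every event is to be followed to resolution, to stabilization, or to completion of the study.

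**The concern.** The route to longer follow-up is narrow. Under section 10.3.1, a UADE is a serious effect that "was not previously identified in nature, severity, or degree of incidence in the investigational plan" or application, or another unanticipated serious problem. Section 10.1 already names "Hypoglycemia, hyperglycemia, diabetic ketoacidosis, seizure, coma or death related to insulin administration", pump use or system use. Sections 10.3.3 and 10.3.4 make severe hypoglycemia and DKA serious by definition. The serious harms most to be expected from an insulin bolus calculator are therefore those least likely to qualify for follow-up beyond Visit 6.

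Safety is the primary objective, and Phase 2, the only phase that tests the calculator, is the last week of participation. A serious event in that week has little time left in which its outcome can be recorded. If it is still open, the final record may show only that it was ongoing. With so few subjects, each such record matters to a reader of the listing.

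The two follow-up limits also leave sites unsure which to apply.

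**Working it through.** There is no sample size, power or alpha figure to reproduce: section 11.2 calls the study non-powered and section 11.5 sets no hypotheses. The check is a comparison of the text, with two short calculations for size.

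**1. When does follow-up end?**

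| Section | Covers | End point |
|---|---|---|
| 10.3.7, UADE sentence | Ongoing UADEs | Resolution or no prospect of change, after completion or withdrawal |
| 10.3.7, next sentence | All other reportable events | Participant's completion; withdrawal not mentioned |
| 10.3.7, ongoing category | Open AEs and SAEs | Final outcome or participant's completion |
| 10.3.2 | All AEs | Resolution, stabilization or completion of the study |
| 8.2.3 | Each subject | Visit 6 |
| 8.4 | Early withdrawals | Participation ends with the withdrawal |

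Section 10.3.2 can be read in two ways. If the study means the whole trial, follow-up may run well past a subject's last visit, since the Protocol Summary expects the trial to take up to 6 months. If it means the subject's own study, as section 8.2.3 uses the word, it agrees with 10.3.7. The text does not settle which.

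**2. What happens at withdrawal?** Under section 10.6.1, if the Medical Monitor judges continued use unsafe after a DKA or severe hypoglycemia event, "use will be discontinued, and the subject will be withdrawn from the study". Section 8.4 then ends participation, and 10.3.2 ends reporting with participation. The cut-off for a withdrawn subject with a non-UADE event is inferred from these two sections. The cut-off sentence in 10.3.7 speaks only of completion.

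**3. How much time does a Phase 2 event have?** Days available = Visit 6 day − onset day. Visit 4, which starts Phase 2, is Day 8 ±1; Visit 6 is Day 14 ±1.

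- Onset at the start of Phase 2: nominal 14 − 8 = 6 days; shortest 13 − 9 = 4; longest 15 − 7 = 8.
- Onset on Day 13: nominal 14 − 13 = 1 day; range 13 − 13 = 0 to 15 − 13 = 2.

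**4. How many subjects might this touch?** The documents give no expected event count, so this is only an illustration. Assume that the Introduction's annual incidence of 11.8% for severe hypoglycemia applies here at a constant rate.

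- Rate λ = −ln(1 − 0.118) = 0.1256 per person-year.
- Expected events = N × days / 365.25 × λ; P(at least one) = 1 − exp(−expected).

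| N | Annual incidence | All 7 days of Phase 2 | Last 2 days |
|---|---|---|---|
| 42 | 11.8% | 0.10 (9.6%) | 0.03 (2.8%) |
| 30 | 11.8% | 0.07 (7.0%) | 0.02 (2.0%) |
| 42 | 18.6% | 0.17 (15.3%) | 0.05 (4.6%) |

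The last row uses the Introduction's figure for diabetes duration above 40 years as a high case. The table counts severe hypoglycemia events of any outcome. Only those still unresolved at the last visit would be affected, so the affected number is smaller. DKA and other serious events are not included.

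**The case against.** The other side has a good deal on its side.

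- **No event is left blank.** One that resolves before the last visit gets its final outcome. One that does not is coded as ongoing. Unknown is reserved for a subject or records that cannot be reached. A reader might infer that late serious events are closed without any outcome; the text does not say that.
- **A listed risk can still be a UADE.** The definition also covers unexpected severity or incidence, and the Medical Monitor decides case by case. Section 10.1 names hypoglycemia, seizure and coma, but not severe hypoglycemia as such.
- **Classification depends little on later course.** DKA and severe hypoglycemia are serious by definition, and section 10.7 has SAEs typically reviewed within 24 hours of reporting. Only one of several grounds for relatedness in section 10.3.5, that the event abates once the device or procedure ends, looks at what happens later.
- **The planned analyses hardly use outcome.** Section 11.6.1 tabulates events by phase, category, seriousness, severity and relationship. The primary endpoints are CGM percentages. The inference that the safety conclusion would rest on incomplete outcomes is therefore not supported.
- **Other sources exist.** Section 10.5 requires that a discharge summary be requested when an SAE involves hospitalization, and that a death certificate be sought. DKA as defined in section 10.3.4 involves treatment in a health care facility. The Safety Management Plan, which is not among the documents, may add more.

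All of this stands, and it limits the point to a small one. It does not remove it. The discharge summary does not cover events managed without admission or recovery after discharge. The protocol still has no stated route to a final outcome for a related serious event that is not a UADE and is open at Visit 6. The differing limits in 10.3.2 and 10.3.7 remain.

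**Conclusion.** The point holds in a narrow form. A serious event related to the device that is not a UADE and is unresolved at Visit 6 may remain coded as ongoing with no final outcome. The same may be true at early withdrawal, but there the cut-off is inferred. Sections 10.3.2 and 10.3.7 need to be reconciled on when follow-up ends.

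The size is small. On the illustrative rates, the chance of any severe hypoglycemia event in the last two days of Phase 2 is about 2% to 5%, and only unresolved events count. Those figures assume that the Introduction's incidence carries over to this sample. Excluding subjects with severe hypoglycemia in the past 6 months may lower the true rate. The wider event definition in section 10.3.3, compared with the seizure or loss of consciousness behind the cited figure, may raise it.

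A reader might go further and conclude that a DKA or severe hypoglycemia event that stops a subject's participation ends the collection of its own outcome. No section says so. The non-UADE sentence in 10.3.7 is silent on withdrawal, and section 8.4 requires an adverse event assessment at the withdrawal visit. The silence is a reason to state the rule; it does not show that outcomes are lost. This is an inexpensive improvement to a safety study and no threat to its planned analyses.

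**What to change.** 1. In section 10.3.7, extend the UADE follow-up sentence to SAEs ongoing at Visit 6 or at withdrawal, at minimum those judged related or possibly related to the device or study procedures. Collect their outcome until they resolve or stabilize, or consent is withdrawn.
2. State that this also applies to subjects withdrawn under section 10.6.1.
3. Use one end-of-follow-up rule in 10.3.2 and 10.3.7, and make clear whether completion refers to the participant or to the whole study.

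The change concerns data collection only and leaves clinical management as it is. It costs protocol wording and occasional telephone calls by existing site staff. The downside is that a few safety records would close after Visit 6.
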